10.0 EVALUATION DURING TREATMENT/INTERVENTION

The focus of the evaluation during the treatment will be directed to assess the safety of the procedures described above.

All patients will be observed for 30 minutes after drug injection to monitor for acute allergic reactions. All participants will be observed in the PACU after cryoablation and/or image guided core biopsies for a couple of hours prior to expected same day discharge if sedation or anesthesia is required.

No additional testing, treatment, or intervention will be performed on patient accrued to the protocol.

Efforts should be made to synchronize post procedure pain management, and to try to avoid NSAIDs (specifically COX-2 inhibitors) given their potential for immune modulation.

11.0 TOXICITIES/SIDE EFFECTS

In routine care for breast cancer, multiple cores are taken to insure adequate material for diagnosis. The potential complication associated with these procedures, such as bleeding and infection are the same as those associated with these procedures when done as part of routine care. Refer to Appendix 2 for management of immune related adverse events.

11.1 Cryoablation

Patients will be monitored for adverse events related to ablation. These events may include bleeding, infection, injury to the breast, skin injury, and pain at the ablation site. Other potential complications include paresthesias.

11.2 Infusion Reactions

Ipilimumab and/or nivolumab may induce infusion or hypersensitivity reactions. If such a reaction were to occur, it may manifest with fever, chills, rigors, headache, rash, pruritus, arthralgias, hypo or hypertension, bronchospasm, or other symptoms. Infusion reactions should be graded according to Common Terminology Criteria for Adverse Events (CTCAE, Version 4.0) guidelines. Treatment recommendations are provided below and may be

modified based on clinical judgment, local treatment standards and guidelines, and/or specific symptoms, as appropriate:

For Grade 1 symptoms: Mild reaction [e.g., localized cutaneous reactions including mild pruritus, flushing, rash] requires infusion rate to be decreased; intervention may be indicated.

- Decrease the rate of the study drug infusion until recovery from symptoms.
- Remain at bedside and monitor subject until resolution of symptoms. Diphenhydramine 50 mg may be administered at the discretion of the treating physician.
- When symptoms resolve, restart the infusion at the original infusion rate.

For Grade 2 symptoms: Moderate reaction [i.e., any symptom not listed above (mild symptoms) or below (severe symptoms) such as generalized pruritus, flushing, rash, dyspnea, hypotension with systolic blood pressure > 80 mm Hg], requires infusion interruption but responds promptly to symptomatic treatment [e.g., antihistamines, nonsteroidal anti inflammatory drugs, narcotics, corticosteroids, i.v. fluids]; prophylactic pre-infusion medications indicated for ≤ 24 hours.

- Discontinue the study drug infusion.
- Begin an i.v. infusion of normal saline, and treat the subject with diphenhydramine 50 g i.v. (or equivalent) and/or paracetamol 325 to 1000 mg (acetaminophen).
- Remain at bedside and monitor subject until resolution of symptoms. Corticosteroid therapy may be administered at the discretion of the treating physician.
- When symptoms resolve, restart the infusion at 50% of the original infusion rate; if no further complications ensue after 30 minutes, the rate may be increased to 100% of the original infusion rate.
- Monitor subject closely. If symptoms recur, immediately discontinue the infusion; no further study drug will be administered at that visit. Administer diphenhydramine 50 mg i.v., and remain at bedside and monitor the subject until resolution of symptoms.
- The amount of ipilimumab infused must be recorded.

For Grade 3 or Grade 4 symptoms: Severe reaction [e.g. bronchospasm, generalized urticaria, systolic blood pressure < 80 mm Hg, or angioedema], Grade 3: prolonged [i.e. requiring 6 or more hours to respond to symptomatic medication and/or discontinuation of infusion]; recurrence of symptoms following initial improvement; hospitalization indicated for other clinical sequelae [e.g., renal impairment, pulmonary infiltrates].

Grade 4: life-threatening; pressor or ventilatory support indicated.

- Immediately discontinue the study drug infusion. No further study drug will be administered. The amount of study drug infused must be recorded on the case report form (CRF).
- Begin an i.v. infusion of normal saline, and treat the subject as follows: Recommend bronchodilators, epinephrine 0.2 to 1.0 mg of a 1:1,000 solution for subcutaneous administration or 0.1 to 0.25 mg of a 1:10,000 solution injected slowly for i.v.

Memorial Sloan Kettering Cancer Center

IRB Protocol #: 16-495 A(5)

Approved: 3-MAY-2017

administration, and/or diphenhydramine 50 mg i.v. with methylprednisolone 100 mg i.v. (or equivalent), as needed.

- Remain at bedside and monitor subject until recovery from symptoms.
- Subject should be monitored until the treating physician is comfortable that the symptoms will not recur.
- Treating physician should follow their institutional guidelines for the treatment of anaphylaxis

In the case of late-occurring hypersensitivity symptoms (e.g., appearance of a localized or generalized pruritus within 1 week after treatment), symptomatic treatment may be given (e.g., oral antihistamine or corticosteroids).

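### Section 11.2 recommends 50 g of i.v. diphenhydramine for a Grade 2 infusion reaction, 1000 times the 50 mg given everywhere else in that section

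*Combined protocol and SAP*

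**What the plan says.** Section 11.2 (Infusion Reactions) of the combined protocol and SAP sets out what to do if ipilimumab or nivolumab provokes an infusion or hypersensitivity reaction, by CTCAE grade. Diphenhydramine appears at four places:

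- Grade 1: "Diphenhydramine 50 mg may be administered at the discretion of the treating physician".
- Grade 2, initial treatment: "treat the subject with diphenhydramine 50 g i.v. (or equivalent) and/or paracetamol 325 to 1000 mg (acetaminophen").
- Grade 2, if symptoms recur after restarting the infusion: "Administer diphenhydramine 50 mg i.v., and remain at bedside and monitor the subject until resolution of symptoms".
- Grade 3 or 4: "and/or diphenhydramine 50 mg i.v. with methylprednisolone 100 mg i.v. (or equivalent), as needed".

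The lead-in fixes the status of this text. The sentence runs across a page break: "Treatment recommendations are provided below and may be" "modified based on clinical judgment, local treatment standards and guidelines, and/or specific symptoms, as appropriate". The list is therefore guidance to the treating physician, not a fixed order.

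**The concern.** The Grade 2 initial-treatment bullet gives the antihistamine in grams, while every other mention in the section gives it in milligrams. Read literally, a moderate reaction would be treated with far more drug than the protocol gives for a life-threatening one.

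This is operative text. Under Sections 4.1 and 9.1 all 6 women are to receive both antibodies by infusion, and Section 10.0 has them observed for 30 minutes afterwards for acute allergic reactions. If a Grade 2 reaction occurs, this bullet is the first drug-treatment step, and it would be consulted at the bedside under time pressure. The toxicity text in Section 3.0 points to a Section 11.3 for supportive treatment of infusion reactions. The document has no such section, so Section 11.2 is the only infusion-reaction treatment guidance the reader will find.

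What is at stake is patient safety in a curative-intent population. Inference is not affected: the endpoint, the decision rule and the descriptive analyses in Section 14.0 do not depend on this line.

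**Working it through.** No design calculation is involved. The check is a comparison of units and amounts within one section.

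**Inputs, all from Section 11.2**

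| Place | Drug | Amount as written | Route stated |
|---|---|---|---|
| Grade 1 | diphenhydramine | 50 mg | none |
| Grade 2, initial | diphenhydramine | **50 g** | i.v. |
| Grade 2, initial | paracetamol | 325 to 1000 mg | none |
| Grade 2, recurrence | diphenhydramine | 50 mg | i.v. |
| Grade 3 or 4 | epinephrine (1:1,000) | 0.2 to 1.0 mg | subcutaneous |
| Grade 3 or 4 | epinephrine (1:10,000) | 0.1 to 0.25 mg | i.v. |
| Grade 3 or 4 | diphenhydramine | 50 mg | i.v. |
| Grade 3 or 4 | methylprednisolone | 100 mg | i.v. |

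**Step 1: convert to a common unit.** 50 g × 1000 mg/g = 50,000 mg.

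**Step 2: ratio to the other mentions.** 50,000 mg ÷ 50 mg = 1000. With the unit changed to mg, the ratio is 50 ÷ 50 = 1.

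**Step 3: count the mentions.** There are four diphenhydramine mentions, three at 50 mg and one at 50 g. Three of the four specify the i.v. route; two of those are at 50 mg and one is at 50 g. The difference is therefore not explained by route.

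**Step 4: count all drug amounts.** Counting a range once, the section states 4 (diphenhydramine) + 1 (paracetamol) + 2 (epinephrine) + 1 (methylprednisolone) = 8 amounts. Seven are in mg and one is in g.

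**Step 5: could the larger amount be intended?** A dose that rises with severity would put Grade 2 between Grade 1 and Grade 3 or 4. Both of those are 50 mg. Within Grade 2 itself, the recurrence bullet comes three bullets after the disputed one and gives 50 mg i.v. No reading by grade, route or stage of treatment produces 50 g.

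**Step 6: could it be an artefact of reading the PDF?** The error amounts to one missing letter, so this cannot be ruled out from the extracted text. Against it, the paracetamol amount in the same bullet kept its mg, and so did every other amount in the section.

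**The case against.** The strongest case on the other side accepts the inconsistency and disputes its weight.

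- **Certainty.** The point rests on one letter in machine-read text. Section 3.0 shows at least one other apparent lost character: a T-cell subset is written as CD with no number after it. That example sits in superscript formatting and may be an author's slip, so it is weak evidence. The objection stands to this extent: the inconsistency is certain in the text supplied, and the source page still needs to be looked at.
- **Label.** Nothing has been miscalculated. This is a unit slip in supportive-care text, not an error in a study computation. That is a fair description, and it changes neither the finding nor the remedy.
- **Weight.** The list consists of recommendations open to clinical judgment and local standards. The bullet itself allows an equivalent drug and offers paracetamol as an addition or alternative. The right dose appears in the grade below, the grade above and the same grade. The trial is at a single institution, with 6 patients and one administration of each antibody. No order set or automated process that would carry the line to a patient is described. All of this is true, and it makes harm unlikely, although the documents give no figure from which a probability could be derived.

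These points limit how far the error reaches. They do not make the written dose right: the freedom to depart from a recommendation is not a reason to leave the recommendation wrong by a factor of 1000.

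**Conclusion.** The concern holds: the dose is wrong as written. The Grade 2 initial-treatment bullet is too high by a factor of 1000 (50,000 mg against 50 mg), in 1 of 4 diphenhydramine mentions and 1 of 8 drug amounts in Section 11.2. The intended value is 50 mg i.v.; this is inferred from the other three mentions and needs no outside source.

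The conclusion assumes that the source page reads as the extracted text does. The number of patients to whom the bullet would apply cannot be stated, because the documents give no Grade 2 infusion-reaction rate for this regimen; by design it is at most the 6 planned patients plus any replacements treated under Section 13.0.

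It should be corrected without fail because it is dosing guidance for trial participants. It is not a threat to the trial's conclusions.

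**What to change.** Check the source page. If it reads as supplied, change the diphenhydramine amount in the Grade 2 initial-treatment bullet of Section 11.2 from 50 g i.v. to 50 mg i.v., so that all four mentions agree. If the line has been copied into an order set or bedside sheet, correct that as well; the documents do not describe one.

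The cost is one added letter in an administrative amendment. Schedule, sample size, endpoint and analysis are unaffected.

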12.0 CRITERIA FOR THERAPEUTIC RESPONSE/OUTCOME ASSESSMENT

12.1 Safety:

Safety/tolerability is the primary end point for this project.

Safety will be evaluated for all treated subjects using National Cancer Institute (NCI) Common Terminology Criteria for Adverse Events v4.0 (CTCAE). Safety assessments will be based on medical review of adverse event reports and the results of vital sign measurements, physical examinations, and clinical laboratory tests. The incidence of observed adverse events will be tabulated and reviewed for potential significance and clinical importance. The reporting period for safety data will be from the date of first on-study dose to 12 weeks after ipilimumab/nivolumab administration.

If there are no clinical signs or symptoms of toxicity, safety bloods will be done every 2-3 weeks and will include the following:

- Comprehensive metabolic panel (COMP): aspartate aminotransferase (AST), alanine aminotransferase (ALT), albumin, alkaline phosphatase (ALP), total bilirubin, calcium, creatinine, glucose, total protein, BUN, sodium, potassium, chloride, bicarbonate
- Complete blood cell count with differential and platelet count (CBC)
- Thyroid stimulating hormone (TSH)

If 5 of the 6 study patients are without an AE necessitating delay in surgery, the regimen will be considered safe/tolerable for further study.

12.2 Efficacy:

Although not a primary endpoint, exploratory correlative studies will be performed to evaluate anti-tumor and immunological response pre- and post-treatment in individuals. Comparisons with other study participants will also be conducted. Breast cancer tissue specimens, axillary lymph nodes specimens where available and peripheral blood samples will be studied. The planned exploratory correlative studies currently include:

Immune response:

The phenotypic and functional impact of the treatment will be explored by examining specimens from tumor tissue; peripheral blood (post treatment only). These tests will be done at the IMF (currently located in the Zuckerman building).

The exploratory objectives of this study are:

1. To evaluate the effect of cryoablation and ipilimumab/nivolumab administration on: lymphocyte phenotype and serum cytokines, disease related biomarkers, antibody responses to selected antigens, and humoral and cellular responses to tumor antigens and recall non-tumor antigens.
2. To examine tumor samples for pathologic correlates of clinical activity before and after treatment, including (but not limited to) the abundance and characteristics of inflammatory infiltrates (e.g., CD8 and CD4 cells and expression of some molecules on lymphocytes and tumors, respectively), and,
3. To evaluate serological and cellular immune correlates of toxicity and/or clinical activity

To this end, the specimens to be collected for IMF evaluation include:

- At least 1 core biopsy sample (collected on the core biopsy date)
- Surgery specimen
- Four research blood samples:
 1. Baseline blood on the day of pre-surgical testing or on the day of ipilimumab/nivolumab injection prior to drug administration
 2. Blood on day of core biopsy/cryoablation
 3. Blood on the day prior to or day of surgery
 4. Blood 30 (+/-10) days after surgery.

For the each blood draw, 4 CPT tubes will be collected.

- **Flow cytometric analysis:**
 - 1) T-cells: activation and memory markers
 - 2) Dendritic cells: activation and maturation markers and markers of inhibitory/tolerogenic DCs
- **ELISA**: to identify relevant peripheral blood cytokines
- **CBC**: to quantify Absolute lymphocyte count (ALC).

Pathology: Pre (core biopsies) and post (surgical tissue) treatment evaluation of the tumor will be performed for each study participant. The planned exploratory studies to evaluate treatment response include:

- Evaluation of T cell proliferation as measured by Ki-67.
- Expression of the B7-H1 inhibitory molecule (Ghebeh 2007)
- Lymphocyte infiltration including perivascular infiltration.
- Specific immunohistochemistry (IHC) staining to further define particular lymphocytic populations such as T-regulatory cells (Tregs) ($CD4^+CD25^+FOXP3^+$), effector T cells (Teff) ($CD4^+/CD8^+$) and the ratio between Tregs and Teff.
- Using immunohistochemistry (IHC) staining to identify subsets of dendritic cell (DC) populations (i.e. tolerogenic versus immunogenic) Sentinel or non-sentinel lymph

node tissue, where available, will also be evaluated by immune profiling as described above.

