The purpose of the study is to determine the safety of pre-operative ipilimumab, nivolumab and cryoablation in patients with biopsy proven resectable breast cancer. If at least 5 of the 6 patients are without an adverse event (AE) necessitating delay in surgery, the regimen will be considered safe/tolerable for further study. Secondary aims of this study are to explore and characterize pre- and post-intervention peripheral and tumor responses to ipilimumab, nivolumab and cryoablation.

Med Onc and Cryoablation Evaluation Appointments

At First Visit For Potential Study Candidates in Surgery Clinic

- Non-study surgery date is scheduled
- Non-study pre-surgical testing date is scheduled
- Informed consent is provided
- Initial Med Onc and Cryoablation Evaluation appointments, if feasible, are scheduled to occur as soon as possible

Med Onc and Cryoablation Evaluation Appointments

- Potential study candidates evaluated for eligibility
- If eligible then:
 - Informed consent signed
 - Core biopsy (+ cryoablation) date set for 7-10 days before surgery
 - Ipilimumab + nivolumab date set for 1-5 days before core biopsy/cryoablation date
 - Post-op follow-up appointment with Med Onc set

Eligibility/Baseline study bloods (coordinated with routine Pre-Surgical Testing whenever feasible) *

Ipilimumab + Nivolumab Date* (1-5 days before biopsy/cryoablation)

Appt. with Med Onc

Ipilimumab + nivolumab administered

Core Biopsy + Cryo Date* (7-10 days before surgery)

Core biopsy x ≥ 3

Cryoablation

Surgery Date*

Safety assessment 2-3 weeks post-surgery (coordinated with off-study surgery follow-up appt if feasible) and then every 2-3 weeks thereafter until at least 12 weeks post ipilimumab and nivolumab date. #

All Arms: Research bloods 30 (+/-10) days after surgery.*

* Indicates time points for obtaining Research blood samples. Baseline study bloods may be drawn with routine pre-surgical testing or on the day of ipilimumab injection (if applicable), prior to drug administration.

Indicates time points for obtaining Safety blood Samples

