2.0 OBJECTIVES AND SCIENTIFIC AIMS

Primary Objective

- To assess the safety and tolerability of pre-operative ipilimumab, nivolumab and intratumoral cryoablation in patients with resectable breast cancer.

Exploratory Objectives:

To evaluate the effect of cryoablation and ipilimumab/nivolumab administration on intratumoral and serum lymphocyte phenotypes, intratumoral and serum dendritic cells (DCs), serum cytokines, disease related biomarkers, antibody responses to selected antigens, and humoral and cellular responses to tumor antigens and recall non-tumor antigens.

- To assess the effect of treatment on ratios of specific intratumoral and serum T cell populations including CD4+FOXP3+ T-regulatory cells (Tregs) and CD8+Effector cells.
- To explore T cell diversity and clonality changes by deep sequencing
- To assess the pharmacodynamic effects of ipilimumab, nivolumab and cryoablation on Absolute Lymphocyte Count (ALC) and absolute T cell count (see below).

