Recent studies have shown that administration of ipilimumab in the pre-operative setting is safe and does not cause delay of surgery in bladder cancer.¹² In this study, ipilimumab and Nivolumab will be administered 1-5 days prior to core biopsy + cryoablation and 8-15 days prior to the planned surgery.

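### Section 12.2 calls the cryoablation-day core biopsy pre-treatment, but it is taken 1-5 days after ipilimumab and nivolumab, and no drug-naive tumour sample is listed for the correlative studies

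*Combined protocol and SAP*

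**What the plan says.** **Label.** The pathology paragraph of Section 12.2 reads: "Pre (core biopsies) and post (surgical tissue) treatment evaluation of the tumor will be performed for each study participant". Exploratory objective 2 in the same section is "To examine tumor samples for pathologic correlates of clinical activity before and after treatment", and the section opens by saying that the correlative studies will "evaluate anti-tumor and immunological response pre- and post-treatment in individuals".

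**Specimens.** The Section 12.2 list for the immune monitoring facility has two tumour items. One is "At least 1 core biopsy sample (collected on the core biopsy date"; the other is the surgical specimen. The list also has four blood draws, the first of them before dosing.

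**Timing.** Section 4.2 says that "ipilimumab and Nivolumab will be administered 1-5 days prior to core biopsy + cryoablation and 8-15 days prior to the planned surgery". The schema in Section 1.0 has "Ipilimumab + nivolumab date set for 1-5 days before core biopsy/cryoablation date". Section 9.0 gives the same order, with biopsy and cryoablation 7-10 days before surgery. Appendix 1 puts the infusion at Visit 4 and the core at Visit 5.

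**Purpose.** One exploratory objective in Section 2.0 is "To assess the effect of treatment on ratios of specific intratumoral and serum T cell populations". Section 14.0 will plot tumour biomarkers and the Treg-to-CD8 ratio over the study timepoints, descriptively.

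**The concern.** A sample labelled *Pre* is read as the untreated state. Here it is tissue from a patient who received two checkpoint antibodies 1-5 days earlier. If Section 12.2 is followed as worded, a post-drug value will stand as the before-treatment tumour value for T cell Ki-67, B7-H1, regulatory and effector T cells, and dendritic cells. Any early drug effect in the tumour would then already be in the baseline and would drop out of the reported change.

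Time since infusion at that baseline also varies between patients, and Section 12.2 adds: "Comparisons with other study participants will also be conducted". Section 14.0 says that a larger trial will follow if the regimen is deemed safe, so a mislabelled baseline could be carried into its rationale.

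**Working it through.** **1. Reproduce the plan's own interval.** Inputs: infusion to core, 1-5 days (Sections 1.0, 4.2, 9.0); core to surgery, 7-10 days (Sections 1.0, 4.2, 9.0). Infusion to surgery is the sum:

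- shortest: 1 + 7 = 8 days
- longest: 5 + 10 = 15 days

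This matches the 8-15 days in Section 4.2, so the timing passages agree with one another.

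**2. Can the core precede the drugs?** In whole days there are 5 × 4 = 20 allowed schedules. In every one the core falls 1 to 5 days after infusion; in none does it fall on or before the infusion day.

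**3. What does treatment mean here?**

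- Sections 2.0 and 12.2 define the exploratory objectives by the effect of cryoablation together with ipilimumab/nivolumab.
- Section 1.0 states the secondary aims as pre- and post-intervention responses to all three components.
- Section 14.0 puts the start of the regimen about 15 days before surgery. That fits the infusion (8-15 days) and not the core (7-10 days).

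Treatment therefore starts at infusion. Where the protocol means before cryoablation, it says so: Section 4.2 and the heading of Section 9.2 both call these cores pre-cryoablation.

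**4. What does each listed tumour sample represent?**

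| Sample | Days since infusion | Drugs given | Cryoablation done |
|---|---|---|---|
| Core | 1-5 | yes | no |
| Surgical specimen | 8-15, if surgery is on schedule | yes | yes |

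Neither of the two is drug-naive. Of the four listed blood draws, one is. The core-to-surgery change covers 7-10 days and leaves out the first 1-5 days after infusion. Two patients can differ by up to 5 − 1 = 4 days since infusion at the core. These figures describe the sampling schedule; they do not estimate bias.

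**5. How many patients?** At most six. Sections 4.2 and 9.2 ask for at least three cores if feasible, send two to routine pathology and the additional ones to research, and do not make a patient ineligible if fewer than three are obtained. Three cores leave 3 − 2 = 1 for research; two leave none.

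**The case against.** The strongest reply is that *Pre* is shorthand. Section 4.2 explains that the core is taken then because cryoablation will destroy most of the tumour, and the visit order is disclosed in several places. Section 14.0 plans no change-from-baseline estimate and no test. On a plot over study timepoints, the core would appear after the infusion. Pre-drug diagnostic tissue normally exists (Section 4.2), the centre must confirm the pathology (Section 6.1), and the specimen list is worded as inclusive, so it does not bar use of that tissue.

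Much of this stands. The schedule is not hidden, the analysis is descriptive, and it would be wrong to infer that no drug-naive tissue exists or that none may be used. What the documents support is narrower: none is listed, and no passage assigns diagnostic tissue to the correlative studies.

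The shorthand reading does not fit Section 12.2 itself, which speaks of treatment and pairs the core with surgical tissue as before and after it, while the objectives define treatment to include the drugs. A plot shows the order of samples but does not correct a label that calls one of them untreated.

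**Conclusion.** The point holds as a minor one. The core is post-drug and pre-cryoablation, and the core-to-surgery change cannot be presented as a before-versus-after change for the full regimen.

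It rests on two readings: that the core biopsies in the pathology paragraph are those taken on the core biopsy date, which is the protocol's own term, and that treatment includes the antibodies, as the objectives state. The primary endpoint, the 5-of-6 rule and the figures in Section 14.0 are unaffected.

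Two stronger inferences are tempting and unsupported. The first is that the tumour results will be biased by some known amount or in a known direction; the documents give no intratumoral time course for the first 1-5 days. The second is that, once relabelled, the change isolates cryoablation. It does not: the drugs may still be acting between core and surgery, and there is no control arm.

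**What to change.** 1. In Section 12.2, relabel the core as post-drug and pre-cryoablation, and reword exploratory objective 2 to match.
2. Report core-to-surgery change as change from a post-drug, pre-cryoablation sample to surgery, reflecting cryoablation plus continuing drug effect and not cryoablation alone.
3. Show tumour values by actual days since infusion, including when participants are compared.
4. Make no before-treatment claim for tumour unless pre-drug diagnostic tissue is actually analysed. If it is, report its date relative to infusion.

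Items 1 to 3 change wording and a plot axis. They use the dates of Visits 4, 5 and 7 in Appendix 1 and need no new sample, procedure or visit. The scientific cost is that the intratumoral part of the Section 2.0 objective is then only partly addressed. Using diagnostic tissue under item 4 is optional. The documents do not establish that spare tissue is available, and such a baseline could be incomplete across six patients and come from differently handled material.
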